### 4.0 Treatment Assignment/Randomization

**Recruitment** - Parents of all eligible infants will be approached by research investigator to discuss about the study & research protocol in detail. All questions & concerns will be answered in very simple language & parents will be given written consent form to read. Within 24 to 48 hours, the parents will be approached again to discuss & explain any question they have. We expect around 70 - 75% success in the recruitment. Every year, we deliver around 50 infants ( $\leq$ 30 weeks' gestation). We hope to recruit our desired sample of 42 infants (14 in each study group) within 12 months.

**Sample size:** 14 preterm infants will be randomized to each group (total sample 42) A sample size of 14 at each group (low, median, and high dose) for efficacy endpoint will reach a power of 0.80 to detect an effect size of 0.5 based on one-way ANOVA with a 0.05 significance level. A sample size of 11 at each group for safety endpoint will reach a power of 0.92 at a 0.05 significant level for an equivalence test of means using two onesided tests, when the true difference between the means is 0.0 mmHg, the standard deviation is 10.0 mmHg, and the equivalence limits are -15.0 mm Hg and 15.0 mmHg.

**Randomization:** Adaptive randomization method will be used – each new participant will be sequentially assigned to a particular treatment group by taking into account the previous assignments of participants. For example, first recruit will be Group 1, second Group 2, third Group 3, fourth Group 1 and so on. The study will be blinded to the nurses and parents. If patients complete 12/14 doses of the treatment, they will be analyzed in the treatment arm.

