### Rationale:

Children with urea cycle defects have been treated with L-citrulline for decades and showed no evidence of toxicity. Previous studies in literature have not reported any significant adverse effects. The benefit of treatment (helping treat or prevent BPD\_PH) far outweighs the risks since this condition is associated with significant morbidity/mortality and no preventative measures exist at this time. The study drug has already been tested on animal models and there are no alternatives to studying the safety, efficacy and dosing in preterm infants.

ICH E6 defines an AE as any untoward medical occurrence in a patient or clinical investigation subject administered a pharmaceutical product regardless of its causal relationship to the study treatment. An AE can therefore be any unfavorable and unintended sign (including an abnormal laboratory finding), symptom, or disease temporally associated with the use of medicinal (investigational) product.

All AEs including local and systemic reactions not meeting the criteria for "serious adverse events" should be captured on the appropriate CRF. Information to be collected includes event description, time of onset, clinician's assessment of severity, relationship to study product (assessed only by those with the training and authority to make a diagnosis, which would include MD, PA, Nurse Practitioner, DO, or DDS), and time of resolution/stabilization of the event. All AEs occurring while on study must be documented appropriately regardless of relationship. All AEs will be followed to adequate resolution.

Any medical condition that is present at the time that the patient is screened will be considered as baseline and will not be reported as an AE. However, if it deteriorates at any time during the study, it should be recorded as an AE.

All AEs must be graded for severity and relationship to study product.

**Severity of Event:** All AEs will be assessed by the clinician using a protocol defined grading system. For events not included in the protocol defined grading system, then the following guidelines will be used to quantify intensity.

- Mild: events require minimal or no treatment and do not interfere with the patient's daily activities.
- Moderate: events result in a low level of inconvenience or concern with the therapeutic measures. Moderate events may cause some interference with functioning.

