- Severe: events interrupt a patient's usual daily activity and may require systemic drug therapy or other treatment. Severe events are usually incapacitating.
- Life threatening: any adverse drug experience that places the patient or subject, in the view of the investigator, at immediate risk of death from the reaction as it occurred, i.e., it does not include a reaction that had it occurred in a more severe form, might have caused death.

Changes in the severity of an AE should be documented to allow an assessment of the duration of the event at each level of intensity to be performed. Adverse events characterized as intermittent require documentation of onset and duration of each episode.

Protocol Grading System for Hypotension:

Mild: Drop in systemic mean arterial pressure (MAP)  $\leq$  10% from baseline

Moderate: Drop in systemic mean arterial pressure (MAP)  $\leq$  25% from baseline

Severe: Drop in mean arterial pressure (MAP) > 25% from baseline

Life threatening: Severe hypotension requiring 2 or more inotropes (Dopamine, Epinephrine, Norepinephrine)

**Relationship to Study Products:** If there is any doubt as to whether a clinical observation is an AE, the event will be reported. All AEs must have their relationship to study product assessed using the terms: associated or not associated. In a clinical trial, the study product must always be suspect. To help assess, the following guidelines are used.

- Associated The event is temporally related to the administration of the study product and no other etiology explains the event.
- Not Associated The event is temporally independent of study product and/or the event appears to be explained by another etiology.

**Serious Adverse Event (SAE)**: An SAE in our study will be defined as an AE that meets one of the following conditions:

- Death during the period of protocol defined surveillance
- Life-threatening event (defined as a subject at immediate risk of death at the time of the event) significant hypotension requiring 2 or more inotropes

- Results in a persistent or significant disability/incapacity: Intraventricular hemorrhage Grade III or more, Necrotizing enterocolitis requiring surgery, Retinopathy of prematurity requiring surgery
- Significant lab abnormalities: Thrombocytopenia < 50,000

All SAEs will be:

- recorded on the appropriate SAE CRF
- followed through resolution by a study clinician
- reviewed and evaluated by a study clinician

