## 8.0 Study Withdrawal/Discontinuation

### **Reasons for Withdrawal**

A study subject will be discontinued from participation in the study if any of the following occur:

- Unacceptable toxicity or adverse event (AE): Drop in systemic mean blood pressure > 25% from baseline
- Unacceptable laboratory abnormalities: Thrombocytopenia < 50,000 not explained by other co-existing conditions
- Intercurrent illness, or other medical condition or situation occurs such that continued participation in the study would not be in the best interest of the subject in the opinion of the treating investigator, for e.g. necrotizing enterocolitis requiring subject to be made NPO.
- Development of any exclusion criteria
- Parents withdraw consent to continue in the research for any reason

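### The plan does not say that the clinicians who make the judgement-based safety calls are blinded to dose, and the allocation rotation lets them infer it

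*Combined protocol and SAP*

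**What the plan says.** Blinding is described once, in section 4.0 under Randomization: "The study will be blinded to the nurses and parents". The same paragraph illustrates assignment as a rotation through Groups 1, 2 and 3 in order of recruitment.

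Section 7.0 (Rationale, and the severity and relationship text that follows) says who judges safety. On severity: "All AEs will be assessed by the clinician using a protocol defined grading system". The only protocol-specific scale shown is for hypotension; other events use general descriptions of mild, moderate, severe and life-threatening. Relationship is to be "assessed only by those with the training and authority to make a diagnosis", as one of two categories: "All AEs must have their relationship to study product assessed using the terms: associated or not associated". The test for the first category is: "The event is temporally related to the administration of the study product and no other etiology explains the event".

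Section 8.0 (Reasons for Withdrawal) includes two criteria that need judgement. One is a condition or situation such that "continued participation in the study would not be in the best interest of the subject in the opinion of the treating investigator". The other is "Thrombocytopenia < 50,000 not explained by other co-existing conditions".

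**The concern.** The people stated to be blinded are largely not the people who produce the judged part of the Aim 2 data. Safety is the first secondary outcome in section 9.0, and there is no untreated group, so differences between doses are the only concurrent safety contrast. Sections 2.0 and 7.0 also set up an expectation of harm: more nitric oxide may lower blood pressure.

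A clinician who believes an infant is on the highest dose may more readily grade an event up, call it associated, or judge that the infant should stop. That could produce or exaggerate a dose gradient in the judged outcomes. It could also make missing Day 7 levels depend on dose, because section 9.0 excludes infants without a blood sample and section 8.0 does not require withdrawn infants to be replaced.

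**Working it through.** **1. The plan's own figures.** The point disputes neither power statement, and both reproduce.
- Safety: equivalence of means by two one-sided t-tests, n = 11 per group, SD 10 mmHg, limits ±15 mmHg, true difference 0, 0.05 per side. Standard error = 10 × √(2/11) = 4.26 mmHg, and 15/4.26 = 3.52. Exact power, integrating over the sampling distribution of the variance with 20 degrees of freedom, is 0.920 (stated 0.92).
- Efficacy: one-way ANOVA, 3 groups of 14, f = 0.5. Noncentrality = 42 × 0.5² = 10.5 on 2 and 39 degrees of freedom; power is 0.803 (stated 0.80).

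Blinding the assessors enters neither formula, so N and power stay as they are.

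**2. Which outcomes depend on judgement.**

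| Outcome | How it is decided | Exposure to dose knowledge |
|---|---|---|
| Relationship to drug (7.0) | Clinician decides whether another cause explains the event | High |
| Severity of events other than hypotension (7.0) | General descriptive categories | High |
| Thrombocytopenia as a reason for withdrawal (8.0) | Numeric cut-off plus attribution | Moderate: the count is measured, the attribution is judged |
| Withdrawal by opinion (8.0) | Treating investigator | High |
| Mean blood pressure, the powered safety endpoint (4.0) | Monitor reading | Low |
| Mild to severe hypotension (7.0) | Percentage fall in mean arterial pressure | Low |
| Plasma and urine assays (5.0) | Mass spectrometry | Low |

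**3. Can the assessors learn the dose?** Two routes are visible.
- Enrolment order: under the illustrated rotation, infants 1, 4, 7 and so on receive the low dose, and the other groups follow in the same way. Research investigators approach parents for consent (4.0), so they are well placed to know the order.
- Volume: section 5.0 uses one strength, 100 mg/mL, for every group. For an assumed 1 kg infant the volumes are 50/100 = 0.5 mL, 100/100 = 1.0 mL and 150/100 = 1.5 mL. Volume and weight together give the group, and no masking of volume is described. Investigators extract the study data from the electronic record (5.0); if dose volume is charted there, they see it.

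**4. Sensitivity at 14 per group.** One changed call moves a group's rate by 1/14 = 7.1 percentage points, and two by 2/14 = 14.3. As an invented illustration, two dose-aware calls would turn 1/14 versus 1/14 into 1/14 versus 3/14 (7.1% versus 21.4%). Fisher's exact two-sided p for that table is about 0.60, so it would alter the descriptive picture without statistically separating the doses.

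**5. The route to missing Day 7 levels.** Section 8.0 discontinues a withdrawn infant from participation, and section 9.0 drops infants with no sample. Against this, Day 7 blood is left over from a routine weekly draw (5.0), and withdrawn infants continue standard care (8.0). Loss of the sample is plausible but not established.

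**The case against.** The strongest reply is that little of what the plan formally tests is at risk. The only between-dose safety test described is equivalence of mean blood pressure, read from monitors. The percentage-based hypotension grades are numeric, and most listed serious events are hard facts: death, surgery, a platelet count. Section 7.0 requires every event to be documented whatever its relationship and tells assessors to treat the study product as suspect, so a dose-aware relationship call shifts a label and does not remove an event. A DSMB reviews safety data every 4 months, including data from withdrawn infants. All of this stands, and it limits the point to the judged outcomes. It does not remove the point: DSMB review does not undo a grade or attribution already recorded, and those calls belong to a stated aim.

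Two uncertainties also stand. Part of section 7.0, between the serious adverse event definitions and the procedures for abnormal laboratory values, was not available for review, so some form of independent event review there cannot be excluded. And nurse practitioners are among the permitted assessors; whether they count among the blinded nurses is unclear.

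A reader might infer that the assessors are unblinded, or that the safety comparison as a whole is compromised. The documents support neither: they are silent on the first, and the powered safety endpoint is largely protected from the second. A reader might also think a dose list held by the pharmacy is enough. It is not, while the rotation and the volume reveal the group.

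**Conclusion.** The point holds in a limited form, as an inexpensive improvement. No available text states that those who grade events other than hypotension, judge relationship, attribute thrombocytopenia or withdraw by opinion are blinded, and the illustrated rotation lets dose be inferred. Those outcomes are open to dose-aware bias, and so, less certainly, is the completeness of Day 7 sampling.

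The size of the bias cannot be derived from the documents; the 7.1 points per changed call show only how sensitive a group of 14 is. The conclusion assumes that the rotation is used as illustrated, that assessors can know enrolment order or volume, and that the unavailable text contains no blinded event assessment. It casts no real doubt on the blood pressure test, the percentage-based hypotension grades or the assays.

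**What to change.** In section 4.0, state that those who grade adverse event severity, judge relationship to the drug and make discretionary withdrawal decisions, including the attribution of thrombocytopenia, are blinded to dose group. To make that effective:

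- Replace the rotation with an assignment list that cannot be inferred from enrolment order, held by the investigational pharmacy, which already prepares each dose.
- Have the assignment passed on by someone who does not grade events. The research nurse named in section 5.0 can do this if kept out of grading.
- Keep dose and volume out of the material the graders use.
- Add an emergency unblinding procedure, with each use recorded.
- If some graders cannot be blinded, name them in the protocol and report relationship and discretionary withdrawals as unblinded assessments.

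Extending the statement to laboratory staff would gain little, since the amino acid assays are read against isotope-labelled internal standards.

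The cost is protocol wording, a new list, an unblinding procedure and separation of the assignment and grading roles. No additional assessor is needed if those roles can be divided among existing staff. N and power do not change, and the withdrawal criteria themselves are left as they are.

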## Dose of study drug -

Low dose 100 mg/kg/day Medium dose 200 mg/kg/day High dose 300 mg/kg/day

[figure not shown]
**When to start study drug -** Study drug will be started when infant has been off of TPN for at least 3 days so that IV arginine in TPN does not interfere.

**Sample collection** - 1 mL of blood will be collected from each subject at 2 time points: before starting citrulline (Day 0) and then after completing 1 week enteral L-citrulline supplementation (Day 7). Discarded blood sample from routine blood draw will be used.

It is standard of care for all preterm infants to get weekly blood draws on Tuesdays for hemoglobin monitoring. We will use discarded blood sample from the Tuesday after being on full feeds (no TPN) and start enteral L-citrulline supplementation on the first Tuesday (Day 1) after off TPN for at least 3 days. After 1 week, supplementation will be discontinued (last dose Monday PM) and discarded blood sample from Tuesday (Day 7) will be used to analyze plasma levels or L-citrulline and L-arginine. Immediately after blood collection, blood will be centrifuged at 4-degree C to extract serum. Serum will be divided into aliquots of 100 microliter & stored at -80-degree C for future use.

1 mL of urine will be collected before starting (Day 0) and then daily thereafter till the last day of L-citrulline supplementation (Day 7). Urine will be collected by placing cotton balls in diapers at around noon  $\pm$  2 hours (in between the 2 doses of study drug).

All sample collection will be part of routine/standard care of the infant and no extra blood draws/invasive procedures will be needed.

Sample collected - (time points)

- \*Discarded blood (for arginine, citrulline & ADMA)
- ^Urine daily for urinary arginine, citrulline, nitrites and nitrates

**\*Enteral L-citrulline** –low, medium or high dose divided into 2 doses via gavage feeding tube i.e. 10% L-citrulline twice daily.

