# Assessment of Subject Compliance with Study Intervention/Investigational Product

Since all doses will directly be administered by the bedside nurse, non-compliance is not applicable to this study. Subjects must receive 12/14 doses to be considered a complete subject.

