### 9.0 Statistical Considerations

Study design: Single-center Pilot dose-ranging study

Study population: Premature infants admitted to the Neonatal intensive care unit at UTMB, Galveston.

Rationale: L-citrulline has been shown to increase NO production in neonatal pigs. The use of L-citrulline in premature infants may help increase NO and prevent pulmonary hypertension that develops due to chronic lung disease. Even though L-citrulline has been used safely in infants and children for urea cycle disorders, its dosage, efficacy and safety have not been evaluated in premature infants. Therefore, a pilot dose-ranging study is essential.

There will be 3 study groups in this Phase I trial:

Group 1 (Low dose): 100 mg/kg/day of L-citrulline Group 2 (Medium dose): 200 mg/kg/day of L-citrulline Group 3 (High dose): 300 mg/kg/day of L-citrulline

Sample size: A sample size of 14 at each group (low, median, and high dose) for efficacy endpoint will reach a power of 0.80 to

detect an effect size of 0.5 based on one-way analysis of variance (ANOVA) with a 0.05 significance level. The sample size calculation was based on the following expected mean  $\pm$  SD citrulline concentrations in plasma according to the study from Schwedhelm et al:

Low dose group:  $19 \pm 4 \ \mu mol/L$ Medium dose group:  $21 \pm 4 \ \mu mol/L$ High dose group:  $45 \pm 5 \ \mu mol/L$ 

Primary outcome:

1. Increase in plasma L-citrulline levels and increased NO production (measured indirectly via urinary breakdown products)

Secondary outcomes:

- 1. To determine safety of enteral L-citrulline supplementation in premature infants.
- 2. To determine the dose of enteral L-citrulline needed to increase plasma level of citrulline > 37 mol/L.

Data will be collected from electronic medical records. Measurements will be recorded in a password protected computer on an excel sheet.

A Data Safety Monitor Board (DSMB) as mentioned in section 7.0 will be reviewing safety data every 4 months.

The data will be analyzed at the end of data collection for all subjects who meet the inclusion criteria. SPSS version 24 will be used for data analysis. SAS procedures, linear models, repeated measures analysis of variance (ANOVA) & logistic modeling for receiver operator curve generation (significance p<0.05) will be used. The UTMB Clinical trials studio will be involved to assist in statistics.

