# Procedure for accounting for any missing, unused and spurious data:

In this pilot study, subjects with missing data on important predictors (lack of blood sample for serum arginine/citrulline levels) will be excluded from analyses.

Selection of subjects to be included in the analyses:

We will follow an intention-to-treat approach in the analyses. The primary variables (plasma arginine, citrulline levels and urinary nitrite, nitrate levels) are continuous data

and the one-way ANOVA will be used to analyze differences amongst the 3 treatment groups from day 0 and day 7. Paired T-test will be used to evaluate differences pre-and post-treatment in individual subjects. The data gathered from daily urinary nitrite and nitrate measurements will be represented in line graphs to represent the trend.

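### Intention-to-treat is declared, but the 12-of-14-dose rule and the blood-sample exclusion conflict with it and can drop assigned infants and their urine data from the efficacy analysis

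*Combined protocol and SAP*

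**What the plan says.** Four statements bear on who is analysed.

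- Section 9.0, selection of subjects: "We will follow an intention-to-treat approach in the analyses".
- Section 9.0, general text: "The data will be analyzed at the end of data collection for all subjects who meet the inclusion criteria".
- Section 4.0, Randomization: "If patients complete 12/14 doses of the treatment, they will be analyzed in the treatment arm". Section 6.0, on compliance, adds "Subjects must receive 12/14 doses to be considered a complete subject". Neither says how an infant with fewer than 12 doses is handled.
- Section 9.0, missing data: "subjects with missing data on important predictors (lack of blood sample for serum arginine/citrulline levels) will be excluded from analyses". The exclusion is not limited to the plasma analyses, and the sample that triggers it (Day 0, Day 7 or either) is not named.

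Other parts of the protocol decide who is caught by these rules. Section 5.0 plans two blood samples, one before treatment "and then after completing 1 week enteral L-citrulline supplementation (Day 7", and urine on Day 0 and daily to Day 7. Section 8.0 lists as a reason for withdrawal "Unacceptable toxicity or adverse event (AE): Drop in systemic mean blood pressure > 25% from baseline", which is the threshold of the top MAP grade in Section 7.0, "Severe: Drop in mean arterial pressure (MAP) > 25% from baseline". Section 8.0 also says that withdrawn infants need not be replaced and that their safety data go to the DSMB.

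**The concern.** Intention-to-treat keeps each infant in the group to which it was assigned. Both restrictions act after assignment, and failing them is partly a consequence of toxicity. An infant withdrawn early for a large fall in blood pressure may have fewer than 12 doses and has no planned second study sample. If withdrawals differ by dose, the groups left for analysis are no longer the groups assigned. The documents do not allow the direction of any resulting bias in efficacy to be worked out.

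Two further things are at stake. Urinary nitrite and nitrate are the measure of NO production in the primary outcome, yet as worded a missing blood sample removes the infant, and so its urine series, from analysis. And because nothing ranks the four statements, more than one analysis set could be defended after the data are seen.

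**Working it through.** **1. The rules applied to four hypothetical infants**

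| Infant | Intention-to-treat | 12/14-dose rule | Blood-sample rule |
|---|---|---|---|
| 14 doses, both samples | in | in | in |
| 14 doses, all urine, no Day 7 blood | in | in | out if Day 7 is a trigger; urine lost too |
| 11 doses, Day 7 blood obtained | in | not in the treatment arm; handling unstated | in |
| 6 doses, withdrawn for a MAP fall >25%, no Day 7 blood | in | not in the treatment arm; handling unstated | out if Day 7 is a trigger; in if Day 0 is enough |

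The statements agree only for the first infant. In the second row the urine loss can cover every numbered day from 0 to 7, which is 8 days.

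**2. Effect on the stated efficacy power**

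Inputs from Sections 4.0 and 9.0: three groups, 14 per group, effect size f = 0.5, significance level 0.05, stated power 0.80. One-way ANOVA power comes from the noncentral F distribution with noncentrality λ = N·f² and degrees of freedom 2 and N − 3.

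- 14 per group: λ = 42 × 0.25 = 10.5, power 0.803. This reproduces the stated 0.80.
- 13 per group: λ = 39 × 0.25 = 9.75, power 0.769.
- 12 per group: λ = 36 × 0.25 = 9.0, power 0.729.
- 11 per group: λ = 33 × 0.25 = 8.25, power 0.685.

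These figures assume equal losses in each group.

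**3. The same check with the plan's own planning means**

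Section 9.0 gives 19 ± 4, 21 ± 4 and 45 ± 5 µmol/L. The grand mean is 28.33. The squared deviations are 87.1, 53.8 and 277.8, so the SD of the means is √(418.7/3) = 11.81. The pooled SD is √((16 + 16 + 25)/3) = 4.36. Hence f = 11.81/4.36 = 2.71, and power is already above 0.999 at 4 per group. On these means the loss of infants costs almost no power for plasma citrulline.

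**4. What keeping low-exposure infants would cost**

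Take the high-dose group at 45 ± 5 and assume, as an extreme, that an infant who stopped early has an off-drug level of 15 to 25 ± 4 µmol/L on Day 7.

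- One such infant of 14: mean (13 × 45 + 15)/14 = 42.9 to (13 × 45 + 25)/14 = 43.6; SD 9.2 to 7.1.
- Two of 14: mean (12 × 45 + 30)/14 = 40.7 to (12 × 45 + 50)/14 = 42.1; SD 11.6 to 8.5.

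The SDs are of the mixture (within-group plus between-group variance). The mean stays above 37 µmol/L in each case, but the spread rises.

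**5. Safety, only if the dose rule were misapplied**

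The documents give no event rate or timing, so both are assumed. Let p be the true rate of severe hypotension, and let events be equally likely after each of 14 doses, with withdrawal at the event. Only events after doses 12 to 14 stay in a 12/14 set, so r = 3/14 = 0.214. The rate seen is p·r/((1 − p) + p·r). For p = 0.05, 0.10 and 0.20 this gives 1.1%, 2.3% and 5.1%. With timing from front-loaded to back-loaded, the ranges are 0.2–1.9% at a true 5% and 1.1–8.5% at a true 20%. These are illustrations, not estimates.

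**The case against.** The strongest defence is that the intended reading is not hard to guess. A 12-of-14-dose set is a sensible adherence set for a pilot that asks which dose brings citrulline above 37 µmol/L. The blood-sample exclusion names arginine and citrulline, so it was probably meant for plasma. On the planning means, losing a few infants hardly changes power. Much of this stands: it limits the size of the problem and is a reason to keep the adherence set. It does not remove the conflict. The dose rule is never labelled as an adherence or per-protocol analysis, the blood-sample exclusion is unqualified, and the analysis paragraph that follows it covers urine as well as plasma.

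A reader might go further and infer that severe hypotension will be dropped from the safety results, because one threshold defines the grade and triggers withdrawal. The documents do not support that.

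- No available text applies either restriction to adverse events.
- Section 7.0 requires every adverse event on study to be documented and serious ones to be reported to the IRB.
- Section 8.0 sends withdrawn infants' safety data to the DSMB, which under Section 9.0 reviews safety data every 4 months.
- Section 7.0 is incomplete in the copy reviewed: Section 9.0 cites DSMB text there that the copy does not contain. A safety set not being visible is therefore weak evidence that none exists.

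Nor can it be said that the blood-sample rule would remove every such infant. A Day 0 sample is planned for all, routine weekly draws are standard care, and the triggering sample is not named.

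**Conclusion.** The inconsistency is real and lies in the stated text. Intention-to-treat, the 12-of-14-dose condition and the unqualified blood-sample exclusion give different analysis sets for any infant who stops early or lacks a sample. Followed literally, the restrictions can take assigned infants out of the efficacy analysis for reasons linked to toxicity and can discard primary-outcome urine data.

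The numerical effect is small to moderate. Power falls from 0.80 to as low as 0.69 if three infants per group are lost at f = 0.5, and hardly at all at the f of about 2.7 implied by the planning means. Which figure applies depends on which effect size is believed, and the second concerns plasma citrulline only, not urine.

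Understated hypotension is a possible misuse that the plan should rule out. It is not a demonstrated error, and the rates shown for it rest on assumed frequency and timing. Severity is minor to moderate.

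**What to change.** 1. In Sections 4.0 and 6.0, remove 12 of 14 doses as the condition for analysis in the treatment arm. Keep it as a labelled on-treatment set, reported alongside the main analysis for the >37 µmol/L question in Specific Aim 3.
2. In Section 9.0, state that each efficacy outcome is analysed by assigned group in all assigned infants with data for that outcome. Limit the blood-sample exclusion to the plasma analyses and say which sample triggers it, so that missing blood does not remove urine data.
3. State that the safety summaries and the MAP comparison include every infant given at least one dose, by assigned group, and count the event that led to withdrawal. If a safety set is already defined in the full Section 7.0, a cross-reference is enough.
4. Report the number of exclusions and the reason for each, by dose group.

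The cost is a few sentences in three places and approval of an amendment before use, as Section 10.0 requires. No new samples or visits are needed. The drawback is that infants with low exposure and a Day 7 sample may lower a group mean and widen its SD, to about the extent shown in step 4 of the working. The on-treatment set is there to address that.
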